10.1 Reference Safety Information

For the purpose of reporting AEs and SAEs, the Investigator Brochure for acalabrutinib contains the RSI.

10.2 Monitoring of Adverse Events

After the signing of the Informed Consent Form (ICF) and prior to the first dose of study drug, all SAEs must be reported.

After the first dose of study drug, all AEs/SAEs, irrespective of attribution of causality, must be reported.

All AEs will be reported until 30 days after the last dose of study drug(s) or the start of a new anticancer therapy (whichever comes first). After this period, investigators should report SAEs or other AEs of concern that are believed to be related to prior treatment with study drug.

All SAEs that occur during the reporting period should be followed to resolution or until the investigator assesses the subject as stable, or the subject is lost to follow-up or withdraws consent. Resolution/stable means the subject has returned to baseline state of health or the investigator does not expect any further improvement or worsening of the event.

The events must be detailed to include diagnostic term, severity, causality in relationship to the study drug, duration, action taken and outcome. The descriptions and grading scales found in the NCI-CTCAE version 4.03 or higher will be utilized for AE reporting.

10.3 Definitions of Adverse Events and Causality

An AE is any unfavorable and unintended sign, symptom, or disease temporally associated with the use of an investigational (medicinal) product, regardless of attribution.

This includes the following:

- AEs not previously observed in the subject that emerge during the protocol-specified AE reporting period, including signs or symptoms associated with CLL that were not present before the AE reporting period
- Pre-existing medical conditions (other than the condition being studied) judged by the investigator to have worsened in severity or frequency or changed in character during the protocol-specified AE reporting period.
- Abnormal laboratory values considered clinically significant by the investigator should be reported as AEs.

The following are NOT considered AEs:

- **Pre-existing condition that has not worsened:** A pre-existing condition (documented on the medical history CRF) is not considered an AE unless the severity, frequency, or character of the event worsens during the study period.
- **Preplanned hospitalization:** A hospitalization planned before signing the ICF is not considered an SAE, but rather a therapeutic intervention. However, if during the preplanned

hospitalization an event occurs, which prolongs the hospitalization or meets any other SAE criteria, the event will be considered an SAE. Surgeries or interventions that were under consideration, but not performed before signing the ICF in the study, will not be considered serious if they are performed after signing the ICF in the study for a condition that has not changed from its baseline level. Elective hospitalizations for social reasons, solely for the administration of chemotherapy, or due to long travel distances are also not SAEs.

- **Diagnostic testing and procedures:** Testing and procedures should not be reported as AEs or SAEs, but rather the cause for the test or procedure should be reported. If a test or procedure is done to rule out a diagnosis, the sign or symptom leading to the test/procedure should be the event term, and the event term should only be updated to the diagnosis if/when the diagnosis is confirmed. Testing and procedures performed solely as screening measures (e.g., routine screening mammography or colonoscopy) should not be reported as AEs or SAEs.
- **Abnormal laboratory results that the investigator considers to not be clinically significant:** Abnormal laboratory results are not AEs unless they are clinically significant. For example, a clinically significant laboratory result is one that requires treatment (for example a blood transfusion for low hemoglobin) or requires a change in study drug (e.g., lowering the dose or withholding study drug while the laboratory finding resolves or stabilizes).
- **Progression of underlying malignancy:** Progression of underlying malignancy will not be reported as an AE if it is clearly consistent with the suspected progression of the underlying cancer. Hospitalization due solely to the progression of underlying malignancy should NOT be reported as an SAE. Clinical symptoms of progression may be reported as AEs if the symptoms cannot be determined as exclusively due to the progression of the underlying malignancy, or if they do not fit the expected pattern of progression for the disease under study.

Symptomatic deterioration may occur in some subjects. Symptomatic deterioration is when progression is evident in the subject's clinical symptoms and the investigator may elect not to perform further disease assessments.

If there is any uncertainty about an AE being due only to the disease under study, it should be reported as an AE or SAE.

Investigators will assess the occurrence of AEs and SAEs at all subject evaluation time points during the study. All AEs and SAEs whether volunteered by the subject, discovered by study personnel during questioning, or detected through physical examination, or other means will be recorded in the subject's medical record and on the AE eCRF.

Disease progression itself is not considered an AE; however, signs and symptoms of disease progression may be recorded as AEs or SAEs.

Each recorded AE or SAE will be described by its duration (i.e., start and end dates), severity, regulatory seriousness criteria, if applicable, suspected relationship to the study drug (see

following guidance), and any actions taken. The causality of AEs to the study drug will be assessed by means of the question: ‘Is there a reasonable possibility that the event may have been caused by the study drug?’ per FDA guidance on safety reporting requirements.

10.4 Definition of Serious Adverse Events

Any untoward medical occurrence that at any dose:

- Results in death
- Is life-threatening (places the subject at immediate risk of death at the time of the occurrence)
- Required inpatient hospitalization or prolongation of an existing hospitalization
- Results in persistent or significant disability/incapacity
- Results in a congenital anomaly/birth defect
- Is an important medical event, that may not be immediately life-threatening or result in death or hospitalization, but based upon appropriate medical and scientific judgment, may jeopardize the subject or may require medical or surgical intervention to prevent one of the other serious outcomes listed in the definition above.

Any death (other than death due to disease progression; see [Section 10.5](#)) occurring within 30 days of the subject receiving study drug, regardless of the subject having discontinued from the study, must be reported as a SAE. Any hospitalization <24 hours or hospitalizations for planned procedures will not be considered an SAE.

10.5 Reporting of Adverse Events

All SAEs must be reported within 24 hours of discovery. All initial SAE reports and follow-up information will be reported using the protocol-specific electronic data capture system, according to the instructions provided in the investigator site file. If electronic SAE reporting is not available, paper SAE forms must be faxed or emailed to Acerta Pharma, BV, Drug Safety, or designee. Acerta Pharma, BV, may request follow-up and other additional information from the investigator (e.g., hospital admission/discharge notes, and laboratory results).

Whenever possible, AEs/SAEs should be reported by diagnosis term not as a constellation of symptoms.

Death due to disease progression should be recorded on the appropriate form in the electronic data capture system. If the primary cause of death is disease progression, the death due to disease progression should not be reported as an SAE. If the primary cause of death is something other than disease progression, then the death should be reported as an SAE with the primary cause of death as the event term, as death is typically the outcome of the event, not the event itself. The primary cause of death on the autopsy report should be the term reported.

Autopsy and postmortem reports must be forwarded to Acerta Pharma, BV, Drug Safety, or designee, as outlined for SAEs above.

If study drug is discontinued because of an SAE, this information must be included in the SAE report.

An SAE may qualify for mandatory expedited reporting to regulatory authorities if the SAE is attributable to the study drug (or if a causality assessment is not provided for the SAE, in which case a default of ‘related’ may be used for expedited reporting purposes) and the SAE is not listed in the current acalabrutinib Investigator Brochure (i.e., an unexpected event). In this case, Acerta Pharma, BV, Drug Safety/Designee will forward a formal notification describing the suspected unexpected serious adverse reaction (SUSAR) to all investigators. Each investigator must then notify his or her IRB of the SUSAR, as required.

Drug Safety Contact Information	
eFax:	PPD
Email:	PPD

10.5.1 Second Primary Malignancies

AEs for malignant tumors reported during a study should generally be assessed as SAEs. If no other seriousness criteria apply, the “Important Medical Event” criterion should be used. In certain situations, however, medical judgment on an individual event basis should be applied to clarify that the malignant tumor event should be assessed and reported as a nonserious AE. For example, if the tumor is included as medical history and progression occurs during the study but the progression does not change treatment and/or prognosis of the malignant tumor, the AE may not fulfill the attributes for being assessed as serious, although reporting of the progression of the malignant tumor as an AE is valid and should occur. Also, some types of malignant tumors, which do not spread remotely after a routine treatment that does not require hospitalization, may be assessed as nonserious; examples in adults include Stage 1 basal cell carcinoma and Stage 1A1 cervical cancer removed via cone biopsy.

The above instruction applies only when the malignant tumor event in question is a new malignant tumor (i.e., it is not the tumor for which entry into the study is a criterion and that is being treated by the investigational product under study and is not the development of new or progression of existing metastasis to the tumor under study). Malignant tumors that—as part of

normal, if rare, progression—undergo transformation (e.g., Richter's transformation of B cell CLL into diffuse large B cell lymphoma) should not be considered a new malignant tumor.

10.5.2 Adverse Events of Special Interest

The following events are adverse events of special interest (AESIs) for subjects randomized to the acalabrutinib-containing combinations arm and must be reported to the sponsors expeditiously (see [Section 10.5](#) for reporting instructions), irrespective of regulatory seriousness criteria or causality:

- Ventricular arrhythmias (e.g., ventricular extrasystoles, ventricular tachycardia, ventricular arrhythmia, ventricular fibrillation)

For study treatment containing biologic products:

- Suspected transmission of an infectious agent by the study drug whereby any organism, virus, or infectious particle (e.g., prion protein transmitting transmissible spongiform encephalopathy), pathogenic or non-pathogenic is considered an infectious agent. A transmission of an infectious agent may be suspected from clinical symptoms or laboratory findings indicating an infection in a subject exposed to a medicinal product. This term ONLY applies when a contamination of the study drug is suspected, NOT for infections supported by the mode of action such as immunosuppression.

10.6 Data Safety Monitoring Plan

The data and safety monitoring plan will involve the continuous evaluation of safety, data quality and data timeliness during the dose escalation phase of Cohorts 1 and 2. During this phase, Acerta and investigators will conduct continuous review of data and subject safety at regular intervals. This will include the review of frequency and severity of AEs and responses on the trial, where applicable, to determine if the risk/benefit ratio of the trial changes. SAEs and responses will also be reviewed by The Ohio State University CCC Data Safety Monitoring Committee (DSMC). The principal investigator will also submit a progress report quarterly that will be reviewed by the committee per the DSMC plan. All reportable SAE will be reported to the FDA and IRB of record as per the policies of the IRB. In addition, at the end of each DLT review period, mandatory safety meetings will be held with the sponsor.

For Cohorts 3 and 4, safety data will be reviewed for the first 3 subjects who complete Cycle 3 in each cohort. The review will be repeated for additional subjects if needed. Unless a safety concern is identified (e.g., dose delays >14 days in CCI enrollment in Cohorts 3 and 4 will continue during the safety review until the desired number of subjects is reached. There are no DLTs defined for this portion of the study. See [Section 5](#) for study drugs and administration guidelines.

11 Withdrawal of Subject from Treatment or Assessment

11.1 Withdrawal of Subjects from Study Treatment

The investigator, in consultation with the medical monitor, may withdraw any subject from study treatment, if, in the investigator's opinion, it is not in the subject's best interest to continue.

Any subject has the right to withdraw from the study at any time. In addition, subjects may be withdrawn from study treatment for the following reasons:

- Completed treatment
- Progressive disease
- Adverse event
- Pregnancy
- Physician decision (includes start of alternative anticancer therapy)
- Treatment withdrawal by subject
- Treatment terminated by sponsor
- Subject lost to follow-up
- Death
- Other

Subjects who discontinue study therapy will continue to be followed on study for follow up of safety ([Section 8.3](#)), disease progression, and survival unless they withdraw consent for further follow-up. Thus, all subjects receiving ≥ 1 dose of study drug will be followed during the immediate post-therapy and long-term follow-up assessments unless the subject withdraws consent for such follow-up to be conducted. The date the subject is withdrawn from study treatment or from the study (including long-term follow-up) and the reason for discontinuation will be recorded and also should be described on the appropriate eCRF.

11.2 Reasons for Study Exit

Reasons for study exit include:

- Death
- Subject lost to follow-up
- Study terminated by sponsor
- Study withdrawal by subject
- AE/SAE

- Other

12 Forms to Be Kept

On-study as well as follow-up data will be recorded on data sheets specific to this study. All study participants will sign a written informed consent, which will describe the objectives of the study and potential risks. All subject data will be identified by subject initials and study code number only. Subjects will not be identified by name.

13 Correlative Studies

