 - B. Response evaluations will be done every 12 weeks from randomization for the first 24 months (with the 4th evaluation shifted to Cycle 12 Day 1 rather than Cycle 13 Day 1, to align with study visits), and then every 24 weeks thereafter. Hematology results must be done within 7 days of CT scans. Bone marrow biopsies/aspirates to confirm a CR must be done within 4 weeks of the CT scan, which showed CR.
 - C. PB samples will be used to evaluate for MRD every 3 cycles (at the discretion of the investigator, in line with scheduled response assessments, per protocol).
 - D. Specific times and tube types for correlative samples are outlined in [Section 13.2](#).
 - E. PK analysis will be performed on the first 8 expansion group patients of Cohort 1. Schedule can be found in [Section 13.3](#).
 - F. If performed as part of relapse analysis
 - G. As outlined in [Section 13.4](#)
 - H. Visits to continue every 6 cycles thereafter (\pm 7 days).
 - I. A safety follow-up (SFU) visit is required for all subjects 30 days (+7) from the last dose of study drug.
 - J. After discontinuation of study treatment for any reason, each subject should be followed until disease progression or the start of alternative anticancer therapy. If disease progression has not occurred at the time of the 30-day SFU visit, discontinuation follow-up (DFU) visits should occur approximately every 12 weeks until disease progression. During this period, subjects will be followed via CT scans every 24 weeks; after 2 years in DFU, CT scans will be yearly. AE and concomitant medication reporting, irrespective of seriousness, ends 30 days after the last dose of study drug(s).
 - K. After disease progression or the start of alternative anticancer therapy, all subjects (unless they have withdrawn consent) will be contacted approximately every 12 weeks by telephone, to assess survival until death or lost to follow up.

Table 12: Schedule of Assessments – Cohort 3

Day	Screening	Treatment Phase & Response Evaluation												SFU	Discontinuation follow-up ¹	Relapse/ Disease Progression	Long-term follow-up	
		Cycle 1		Cycle 2			Cycle 3			Cycles 4 -7	Cycles 10, 13, 16, 19, 22	Cycle 24	Cycle 24 q6 cycles					
		1	15	1	8	15	22	1	8	15	22	1	1	1	1			
Study Windows (days)	-28	±3		±3				±3				±3	±3	±3	±7	+7	±7	±7
Study Drug Administration ¹		CCI																
Acalabrutinib																		
Rituximab																		
Venetoclax																		
Procedures																		

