8.4 Discontinuation Follow-up

After discontinuation of study treatment for any reason (except for death, lost to follow up, or withdrawal of consent), each subject should be followed until disease progression. If disease progression has not occurred at the time of the 30-day SFU visit, discontinuation follow-up visits should occur approximately every 12 weeks until disease progression. During this period, subjects will be followed via CT scans (every 24 weeks), CBC with differential, physical examinations (including vital signs and weight), serum chemistry, peripheral blood MRD (every 6 months for subjects in Cohorts 3 and 4 who will be monitored while off study drugs), and bone marrow biopsy and aspirate (as clinically indicated); after 2 years in discontinuation follow-up, CT scans will be yearly. Refer to the Schedule of Assessments ([Section 8](#)) for a full list of assessments required during this period.

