8.5 Long-Term Follow-up

After disease progression, subjects will be contacted to assess survival status approximately every 12 weeks until death, withdrawal of consent by subject, lost to follow-up, or study terminated by sponsor, whichever comes first.

9 Criteria for Response, Progression, and Relapse

Any subject who has confirmed objective evidence of cancer progression while receiving regimens of acalabrutinib and obinutuzumab; acalabrutinib, venetoclax, and obinutuzumab; or

acalabrutinib, venetoclax, and rituximab should be withdrawn from the study treatment. If there is uncertainty regarding whether there is true cancer progression, the subject may continue study treatment and remain under close observation (e.g., evaluated at 4-week intervals) pending confirmation of progression. In particular, transient worsening of disease early in therapy or during temporary interruption of study therapy (e.g., for drug-related toxicity, surgery, or intercurrent illness) may not indicate cancer progression. In such circumstances, and if medically appropriate, subjects may resume therapy and relevant clinical, laboratory, and/or radiologic assessment can be attempted to document whether tumor control can be maintained or whether cancer progression has occurred.

Criteria for response for CLL and prolymphocytic leukemia (PLL) will utilize the IWCLL 2008 ([Hallek et al. 2008, Table 14](#)) for response, which includes clinical, hematologic, and bone marrow features. Responses will be classified as follows:

Complete response: Requires all of the following for a period of at least 2 months:

- Absence of lymphadenopathy >1.5 cm on physical examination and CT scan
- No hepatomegaly or splenomegaly on physical examination (a CT scan also may be used to assess)
- Normal CBC as exhibited by polymorphonuclear leukocytes $\geq 1,500/\mu\text{L}$, platelets $>100,000/\mu\text{L}$, hemoglobin $>11.0\text{ g/dL}$ (untransfused); absolute lymphocyte count $<4,000/\mu\text{L}$

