12.2.7 Overall Survival (OS)

Overall survival (OS) is defined as the time from the date of first dose to death due to any cause. Subjects who were not known to have died prior to the analysis data cutoff date will be censored as follows:

Situation	Outcome	Date	Event Description/ Censoring Reason
Death on or before data cutoff	Event	Date of death	Death
Exit study prior to data cutoff	Censored	Date of discontinuation from study participation as reported on study exit CRF	Withdrew consent/study terminated by sponsor/study exit
Lost to follow-up prior to data cutoff	Censored	Date subject last known to be alive	Lost to follow-up
No death reported on or before data cutoff	Censored	Date subject last known to be alive	Still on study

OS will be calculated as death date (or censoring date) – the date of first dose + 1.

OS will be analyzed similarly to PFS including a KM plot, as described in section 12.2.3.

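### Protocol 11.2 allows study exit for AE/SAE against the follow-up rules in 11.1 and 8.4, so a later death may go unlearned and be missed in OS, PFS, DOR and the deaths table

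*Protocol*

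**What the plan says.** Protocol 11.1 concerns stopping treatment: "subjects may be withdrawn from study treatment for the following reasons", and adverse event is on that list. It then says that "all subjects receiving ≥ 1 dose of study drug will be followed during the immediate post-therapy and long-term follow-up assessments unless the subject withdraws consent". The same section separates the date of withdrawal from treatment from the date of withdrawal from the study, and states that the latter includes long-term follow-up.

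Protocol 8.4 covers the time before progression. After treatment stops for any reason other than death, loss to follow-up or withdrawn consent, "each subject should be followed until disease progression". Protocol 8.5 starts after progression, with survival contact about every 12 weeks "until death, withdrawal of consent by subject, lost to follow-up, or study terminated by sponsor, whichever comes first". Footnote H of Tables 12 and 13 agrees with 8.5. For Cohorts 1 and 2, footnote K of Table 11 has subjects telephoned "to assess survival until death or lost to follow up", with an exception for withdrawn consent.

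Protocol 11.2 is a separate list, introduced by "Reasons for study exit include". Its items are death, loss to follow-up, sponsor termination, withdrawal by the subject, AE/SAE and Other.

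SAP 12.2.7 censors OS for a subject who leaves the study before data cutoff at the "Date of discontinuation from study participation as reported on study exit CRF". The other two censoring rows of that table, for loss to follow-up and for subjects still on study, use the date last known alive. Protocol 14.6.2 measures OS to death or last follow-up and has no exit-form rule.

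**The concern.** Two sets of instructions apply to a living subject who stops because of toxicity. Under 11.1 and 8.4 that subject stays in follow-up. Under 11.2 the subject can be recorded as having left the study, and the contacts that would detect progression or death then end.

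Leaving because of a serious adverse event plausibly goes with a higher risk of death, so censoring at that point may be informative. A death that is never learned of makes survival look better than it was. The exit-form date adds a smaller problem: it need not be a date on which the subject was known to be alive, so it can credit survival time that nobody verified.

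At stake are secondary, descriptive endpoints (OS, and the death component of PFS and DOR) and the completeness of the table of reported deaths in SAP 13.3. That table belongs to the safety analysis, and safety is the primary objective for Cohorts 3 and 4.

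**Working it through.** **Step 1. Set the end-of-follow-up reasons side by side.**

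| Provision | What ends follow-up | AE/SAE named? |
|---|---|---|
| Protocol 11.1 | Withdrawn consent | No |
| Protocol 8.4 (until progression) | Death, loss, withdrawn consent | No |
| Protocol 8.5; Tables 12 and 13, footnote H (after progression) | Death, withdrawn consent, loss, sponsor termination | No |
| Table 11, footnote K (Cohorts 1 and 2, after progression or new therapy) | Death, loss, withdrawn consent | No |
| Protocol 11.2 | Death, loss, sponsor termination, withdrawal by subject, AE/SAE, Other | Yes |

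For an exit before progression the direct conflict is with 11.1 and 8.4. Section 8.5 and the footnotes matter only afterwards.

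**Step 2. Is study exit just loose wording for stopping treatment?** No. Section 11.1 distinguishes the two, and 11.2 lists death as its own item, so AE/SAE there describes a living subject leaving all follow-up.

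**Step 3. Follow such a subject through the SAP.**
- OS (12.2.7): if the death is known and falls on or before cutoff, it is an event. If not, the subject is censored at the exit-form date.
- PFS (12.2.3): a reported death is an event. Otherwise censoring is at the last adequate assessment. There is no exit-date rule and no row for AE/SAE exit. DOR (12.2.4) follows the same rule.
- Deaths (13.3): all reported deaths are summarised.

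In each case a death is missed only if it is never learned of.

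**Step 4. Which deaths are still caught after exit?** Protocol 10.4 requires deaths not due to progression within 30 days of study drug to be reported even if the subject has left the study. Protocol 10.2 has SAEs from the reporting period followed to resolution or stability, unless the subject is lost or withdraws consent, and asks for later SAEs believed related to study drug. What remains exposed is mainly a death more than 30 days after study drug and not judged related.

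**Step 5. Illustrate the size.** The plan states no figure to reproduce, and the documents do not give the number of AE/SAE exits. One or two missed deaths per cohort is an assumption. Cohort sizes are 26 and 19 (Protocol 14.4) and 12 each for Cohorts 3 and 4 (Protocol 14.2).

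Let n be the cohort size, k the exited subjects who later die unknown to the study, and d other deaths, all observed after those exits. With no other censoring before the landmark, the Kaplan-Meier estimates are:
- all deaths known: (n − k − d)/n
- k subjects censored at exit: (n − k − d)/(n − k)

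| n | k | d | All known | Censored at exit | Difference (points) |
|---|---|---|---|---|---|
| 26 | 1 | 0 | 96.2% | 100% | 3.8 |
| 19 | 1 | 0 | 94.7% | 100% | 5.3 |
| 12 | 1 | 0 | 91.7% | 100% | 8.3 |
| 26 | 1 | 2 | 88.5% | 92.0% | 3.5 |
| 19 | 1 | 2 | 84.2% | 88.9% | 4.7 |
| 12 | 1 | 2 | 75.0% | 81.8% | 6.8 |
| 26 | 2 | 0 | 92.3% | 100% | 7.7 |
| 19 | 2 | 0 | 89.5% | 100% | 10.5 |
| 12 | 2 | 0 | 83.3% | 100% | 16.7 |
| 26 | 2 | 2 | 84.6% | 91.7% | 7.1 |
| 19 | 2 | 2 | 78.9% | 88.2% | 9.3 |
| 12 | 2 | 2 | 66.7% | 80.0% | 13.3 |

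If the deaths become known by cutoff, the difference is zero.

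**The case against.** The strongest reply is that 11.2 authorises nothing. It is a bare list of recordable reasons, while 11.1 and 8.4 are the operative rules, so a site that ended survival follow-up for toxicity alone would breach them. That is a fair reading of which text should prevail. But the list still offers the code, and the SAP has an exit row that accepts it without distinction. The documents do not say how the two are to be reconciled.

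A reader might infer more: that the plan removes deaths after toxicity from OS and PFS, or that such deaths escape the 30-day reporting rule. The documents do not support either. SAP 12.2.7 counts any known death on or before cutoff, with no exclusion for earlier exit. Protocol 10.4 applies expressly to subjects who have left the study, so early deaths from toxicity are the best protected. PFS is affected only through lost follow-up.

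It is also true that no decision rests on these endpoints. The criterion for a promising result in Cohorts 1 and 2 is ORR, SAP 7.1 states that no formal hypothesis tests will be done, and there is no comparator arm. This limits the importance of the point. It does not remove the contradiction or the possible gap in the deaths table.

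Finally, deleting AE/SAE alone would leave Other as an equally open code, and the exit date is defensible for consent withdrawal, which is normally a contact. The fix below allows for both.

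**Conclusion.** The contradiction between 11.2 and the follow-up rules in 11.1 and 8.4 (and in 8.5 and the footnotes after progression) is real. SAP 12.2.7 also handles a study exit less well than its own rows for loss to follow-up and for subjects still on study. The consequence is conditional: a subject must be exited under this code, must die later, and the death must never be learned of. Most exposed are deaths beyond 30 days after study drug and not judged related.

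Under those conditions, and with no other deaths or censoring, one missed death raises the survival estimate by about 3.8, 5.3 or 8.3 points (n = 26, 19, 12). The count of such exits is unknown, so these figures show sensitivity and are not an estimate of bias. The effect is confined to OS, the death component of PFS and DOR, and the completeness of the deaths table. The ORR analysis is not directly touched. It is a modest point, worth correcting because the correction is cheap.

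**What to change.** 1. Reconcile Protocol 11.2 with 11.1, 8.4 and 8.5 so that AE/SAE is a reason for ending treatment, as 11.1 already has it, and does not end progression or survival follow-up. Align the study-exit form's code list.
2. For any subject already exited for AE/SAE or Other without withdrawn consent, obtain vital status at data cutoff.
3. In SAP 12.2.7, censor exits other than consent withdrawal at the date last known alive, and state that deaths learned of after exit and dated on or before cutoff count as events.
4. Report study exits by reason and cohort, so that a reader can see how many subjects the point concerns.

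The cost is one list item, a form code, one SAP row with a clarifying sentence, a short disposition table and vital-status checks at a single site for whatever subjects were exited this way. The PFS and DOR censoring rules need no change, since a death that becomes known already counts.
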